4.6 Withdrawal Procedure

When a subject withdraws from the study or if a subject is withdrawn by the investigator, all assessments normally required at the completion of the study will be obtained, where possible. All details available will be reported and recorded. If the reason for removal of a subject from the study is an adverse event, intercurrent illness, surgical intervention or an abnormal laboratory value considered a clinically significant abnormality, i.e., requiring medical intervention or treatment, the specific event will also be recorded. All AEs are intended to be followed through until resolved or stabilized or until the follow-up period is complete.

Case report forms are required for all subjects who are screened. Subjects who sign an informed consent and undergo any procedures for the study, including those who are subsequently excluded or withdrawn from the study before randomization will be documented on the site's screening log. Whenever possible, all sections of the screening worksheets and relevant case report forms, up to the time of withdrawal, should be completed. If applicable, efforts should be made to obtain complete information regarding safety.

If during the course of the study a subject chooses to revoke his/her written authorization for the use and disclosure of personal health information (PHI; per HIPAA privacy ruling or other country and/or region specific law), the subject will then be withdrawn from the study as well (i.e., participation in the MSB-DR003 study is contingent upon an "active" written PHI use, collection, and disclosure authorization) and only safety data will be collected as required by applicable laws. PHI collected prior to the date that the subject revokes his/her written authorization may still be used. If a subject decides to withdraw from the study, he/she should be asked if he/she can still be contacted for further information. The outcome of that discussion should be documented in the medical records.

If a subject decides to withdraw or is withdrawn from the study, the investigator will promptly notify the blinded CRA, or designee, and the reason for and date of withdrawal from study must be recorded.

4.6.1 Lost to Follow-Up

A subject is considered to have been lost to follow-up if he/she is unable to be contacted by the investigator post-randomization. The investigator should show "due diligence" by documenting in the source documents steps taken to contact the subject, e.g., dates of telephone calls or registered letters. The end of participation for a subject lost to follow-up is the date of the last known contact (e.g., visit or telephone contact).

4.7 End of Study

The end of study is defined as the date of the last follow-up visit or the date at which the last data point occurs for the last subject.

5. INVESTIGATIONAL PRODUCT

5.1 Investigational Product Labeling

The product label will contain the elements for investigational products required by 21CFR, 312.6 and other applicable regulatory agencies.

5.2 Description of Investigational Product

5.2.1 Active Treatment

Rexlemestrocel-L cells are STRO-3 selected allogeneic MPCs, which are derived from adult bone marrow mononucleated cells that are immunoselected, culture-expanded, and subsequently cryopreserved.

rexlemestrocel-L alone

Subjects enrolled in the "rexlemestrocel-L alone" arm will receive 1 injection of approximately 6 million rexlemestrocel-L cells in freeze media mixed in a 1:1 by-volume ratio with saline. A vial with 2mL of thawed rexlemestrocel-L cells and freeze media will be mixed with 2mL of saline. Two milliliters of the resulting mixture will be injected, under fluoroscopic imaging, via pressure manometer syringe into the nucleus pulposus of the index level.

rexlemestrocel-L + HA

Subjects enrolled in the "rexlemestrocel-L + HA" arm will receive 1 injection of approximately 6 million rexlemestrocel-L cells in freeze media mixed in a 1:1 by-volume ratio with 1% hyaluronic acid (HA) solution. A vial with 2mL of thawed rexlemestrocel-L cells and freeze media will be mixed with 2mL of 1% HA solution. Two milliliters of the resulting mixture will be injected, under fluoroscopic imaging, via pressure manometer syringe into the nucleus pulposus of the index level.

5.2.2 Control Agent

Subjects enrolled in the control arm will receive a saline injection. Two milliliters of thawed saline from one vial will be mixed with 2mL of thawed saline from another vial of saline. Two milliliters of the resulting saline mixture will be injected, under fluoroscopic imaging, via pressure manometer syringe into the nucleus pulposus of the index level.

5.3 Investigational Product Storage

Rexlemestrocel-L will be shipped just prior to treatment procedures in the vapor phase of liquid nitrogen at \leq -140°C to -196°C until it is ready for use. Additional details regarding the storage and preparation of rexlemestrocel-L are contained in the study materials provided to the site.

Hyaluronic acid will also be shipped directly to the study sites. Once received by the study sites, HA should be stored in accordance with the HA product labeling.

Saline will also be shipped in a cryopreserved container, similar to rexlemestrocel-L. In order to minimize the potential for unblinding, saline should be stored under similar conditions to that of rexlemestrocel-L.

Any IP provided by the sponsor should be stored in a secure location with limited access to the unblinded designees assigned to the study. Blinded designees should not have access to IP.

5.4 Investigational Product Preparation and Administration

5.4.1 rexlemestrocel-L

The vial, in which the rexlemestrocel-L is supplied, will be removed from a shipping container and immersed with gentle shaking in a 37°C water bath. With gentle agitation, the cells will be thawed after approximately 6-8 minutes of submersion and just before the last crystal of ice has fully melted. Once the product is thawed, a timer should be started and run until the time the product is applied to the study subject.

Warning:

If the treatment is not injected within 75 minutes from the start of thaw, product cannot be administered.

5.4.2 All Investigational Product

Refer to the Investigational Product (IP) Manual for details regarding product handling and preparation. A detailed description of the process of injecting the investigational and control materials is also included in the IP Manual.

5.4.3 Investigational Product Handling and Accountability

All investigational product accountability records including records of randomization assignment will be maintained by the unblinded qualified designee, stored in a secure location and reviewed during monitoring visits by the unblinded CRA.

If the rexlemestrocel-L alone, or rexlemestrocel-L + HA is prepared, but not used for whatever reason, the circumstances will be recorded in the accountability $\log/form(s)$ and destruction of investigational product container will occur per the site's policy once accountability by the unblinded CRA has been performed.

The final disposition of all investigational product, whether used or discarded, must be recorded. The final disposition of all unused, empty, and partially used vials will be handled in accordance with the institution's policy and the supplied study materials.

An unblinded CRA will be responsible for reconciliation of IP accountability throughout the study and at study completion.

5.5 Maintenance of the Treatment Blind

Due to the appearance, configuration, and storage conditions of rexlemestrocel-L, saline, and HA, it is not possible to blind all personnel at the investigational study site.

In order to maintain the blind, each site will have an unblinded designee(s) (identified by the investigator) who receives all investigational and control product, performs accountability, properly stores it in a secure location, and prepares the injection. Additionally, the health care professional who is performing the study treatment injection will be unblinded. The unblinded health care professional who is performing the study treatment injection will perform all required procedures and evaluations associated with the treatment injection, including neurological exam prior to discharge, but will not be involved with any subject care or assessment beyond the subject's discharge following the injection procedure. All other site personnel, specifically those administering subject assessments and care, will be blinded to the treatment as will the subjects, radiographic evaluators, and members of the study team, with the following exceptions: unblinded CRAs (responsible for IP reconciliation) and unblinded statistician(s) (responsible for providing data for the interim analysis and DSMB data). Prior to the treatment administration visit, both blinded and unblinded personnel can perform screening activities.

Care should be taken to ensure that the subject does not know which investigational product he/she is receiving. Additionally, care should be taken to ensure that blinded personnel at the site and CRO are not unblinded to treatment assignment. All unblinded study site personnel will be specifically instructed to refrain from discussing any potentially unblinding information with either the subject or any blinded site, sponsor, or CRO personnel involved in the trial. Additional information is provided in the Blinding Plan.

Independent blinded radiologists will be evaluating radiographic images for key inclusion/exclusion criteria to maintain consistency and for radiographic endpoints. Two independent and blinded radiologists will review screening radiographic images to confirm subjects meet the radiographic inclusion/exclusion criteria with a third independent and blinded radiologist will adjudicate any differences between the two initial radiologist's reviews. Follow-up evaluation of radiographic images will be performed by at least 2 blinded independent radiologists with a third radiologist to adjudicate any differences between two initial radiologists with a third radiologist to adjudicate any differences between two initial radiologists with a third radiologist to adjudicate any differences between two initial radiologists with a third radiologist to adjudicate any differences between two initial radiologists with a third radiologist to adjudicate any differences between two initial radiologists reviews' assessments.

Any Interim analyses will be conducted by an unblinded independent statistician.

The DSMB will also be unblinded in order to assess the safety of IP.

The Treatment Events Committee (TEC), performing adjudication of post-treatment interventions and relationship of adverse events to product and/or procedure will be blinded.

When the unblinded statistical analyses are conducted at the conclusion of the primary safety and efficacy evaluation period, study subjects, as well as site personnel responsible for subject care and assessment, will continue to be blinded until the completion of the long-term safety and efficacy follow-up period (i.e., when all subjects who remain active in the study have completed their 36-month treatment visit).

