3.2 Dosing Regimen

Each treatment solution will be prepared by an unblinded designee(s) who is otherwise not involved in study participation after the treatment injection. The health care professional administering the injection will be unblinded to the treatment administered. All other study staff, as well as each study subject, will be blinded to study therapy until the end of the study. Eligible subjects will be randomized to receive 1 of 3 treatments:

- Rexlemestrocel-L alone: One injection of approximately 6 million rexlemestrocel-L cells in freeze media mixed in a 1:1 by-volume ratio with saline. A vial with 2mL of thawed rexlemestrocel-L cells and freeze media will be mixed with 2mL of saline. Two milliliters of the resulting mixture will be injected via pressure manometer syringe into the nucleus pulposus of the index level.
- Rexlemestrocel-L + HA: One injection of approximately 6 million rexlemestrocel-L cells in freeze media mixed in a 1:1 by-volume ratio with 1% hyaluronic acid (HA) solution. A vial with 2mL of thawed rexlemestrocel-L cells and freeze media will be mixed with 2mL of 1% HA solution. Two milliliters of the resulting mixture will be injected via pressure manometer syringe into the nucleus pulposus of the index level; OR
- Saline: One injection of 2mL of thawed saline from one vial will be mixed with 2mL of thawed saline from another vial of saline. Two milliliters of the resulting saline mixture will be injected via pressure manometer syringe into the nucleus pulposus of the index level.

Treatment assignment will occur in sequential chronological order according to a central master list of random assignments. Randomization will be stratified

CONFIDENTIAL

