3.3 Study Sites

In order to enroll approximately 360 subjects, up to 45 study centers in the US, Australia, and potentially the EU will participate.

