9.2 Sample Size and Randomization

Approximately 360 subjects will be enrolled in a randomization ratio of 1:1:1, with each subject assigned to the rexlemestrocel-L alone, rexlemestrocel-L + HA, or saline control group. Randomization will be stratified by study site and opioid use at baseline (opioid users vs. opioid non-users).

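### Unblinded staff who hold a site's earlier assignments may screen later subjects; if blocks are small or fixed, they could partly anticipate the next arm

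*Combined protocol and SAP*

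**What the plan says.** Section 5.5 gives an open permission: "Prior to the treatment administration visit, both blinded and unblinded personnel can perform screening activities". The synopsis entry on blinding says the same.

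Two kinds of unblinded staff are described.

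- **The designee.** Under Section 5.4.3, "All investigational product accountability records including records of randomization assignment will be maintained by the unblinded qualified designee".
- **The injector.** Section 5.5: "Additionally, the health care professional who is performing the study treatment injection will be unblinded".

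Sections 5.5 and 6.5 keep the injector out of a subject's care and assessment after that subject is discharged. Section 3.2 says that those who prepare treatment have no part in the study after the injection. Neither rule addresses the screening of the next subject.

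On allocation, Section 3.2 says: "Treatment assignment will occur in sequential chronological order according to a central master list of random assignments". Section 6.1.2 confirms a central system. Section 9.2 adds: "Randomization will be stratified by study site and opioid use at baseline". The available text gives no block size and does not say whether blocks are used. The last sentence of Section 3.2 breaks off in the extracted text. The SAP and the Blinding Plan are cited, but their text is not in the file available for this review.

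**The concern.** Central allocation hides the list of future assignments. It does not hide past assignments from someone who keeps the record of them. If the list is balanced in short runs within each stratum, past assignments carry information about the next one. A person with that information who also takes part in screening could, knowingly or not, affect who is entered and when.

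The imaging criteria are protected, because blinded core-laboratory radiologists read them. Judgement at the site remains in:

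- the SI-joint examination (Section 6.4.6) and the neurological examination (Section 6.6.3), where a blinded evaluator is preferred before the diagnostic injection but not required;
- exclusions 18 and 25 (Section 4.2.2);
- re-screening, allowed twice at the investigator's discretion (Section 4.4);
- the timing of randomization within the 75-day screening period (Section 6.1.1).

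At stake is comparability of the arms at entry. The ITT set keeps everyone who was randomized, but it cannot correct for selection before randomization. The primary comparison in Section 9.6.2 is described as a comparison of responder rates by arm, with no adjustment for baseline covariates stated.

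**Working it through.** The plan states no predictability figure, so there is none to reproduce.

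**1. Stratum size.** Section 9.2: "Approximately 360 subjects will be enrolled in a randomization ratio of 1:1:1". Section 3.3: "up to 45 study centers in the US, Australia, and potentially the EU will participate". Opioid use has two levels.

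- Strata: 45 × 2 = 90 at most.
- Mean per site: 360 / 45 = 8.
- Mean per stratum: 360 / 90 = 4.

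Fewer sites would mean larger strata.

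**2. Assumptions.** Permuted 1:1:1 blocks of fixed size 3, 6, 9 or 12 are used within each stratum. The guesser knows the block size and every earlier allocation in the stratum, and always names the arm with most places left in the block.

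**3. Formula.** At each position, the chance of a correct guess is the expected value of (largest number of places left in any arm) / (total places left in the block). For the first four subjects:

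- Block 3: (1/3 + 1/2 + 1 + 1/3) / 4 = 2.167 / 4 = 54%
- Block 6: (1/3 + 2/5 + 1/2 + 8/15) / 4 = 1.767 / 4 = 44%
- Block 9: (1/3 + 3/8 + 3/7 + 25/56) / 4 = 1.583 / 4 = 40%

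Unrestricted randomization gives 33% at every position.

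**4. Larger strata**, by exact enumeration (share of allocations that are certain in parentheses):

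| Subjects in stratum | Block 3 | Block 6 | Block 9 | Block 12 |
|---|---|---|---|---|
| 4 | 54% (25%) | 44% (0%) | 40% (0%) | 38% (0%) |
| 8 | 56% (25%) | 51% (15%) | 47% (4%) | 42% (0%) |
| 12 | 61% (33%) | 56% (20%) | 49% (11%) | 51% (11%) |

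An allocation is certain only when two arms are used up. With blocks of 6 that takes at least four earlier subjects, and with blocks of 9 at least six, so a stratum of 4 contains no certain allocation under either. If stratum sizes vary as a Poisson variable with mean 4 (an assumption), the rates are about 56%, 47% and 42% for blocks of 3, 6 and 9, with 25%, 7% and 1% of allocations certain.

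**5. Illustration of the consequence.** Suppose there is no true effect, but selection makes the responder rates p₁ and p₂ of two arms differ by 5 points, from a base of 20% to 40%. With 120 per arm (Section 3.1) and one-sided 0.0125 (0.025 / 2), the chance that the comparison favors the active arm is Φ[(0.05 − 2.241·√(2p̄(1−p̄)/120)) / √((p₁(1−p₁)+p₂(1−p₂))/120)], where p̄ is the mean of p₁ and p₂. At a base of 20%, 30% and 40% this is 9.4%, 7.8% and 7.2%, against a nominal 1.25%. The 5-point shift is assumed; nothing in the documents indicates that it would occur.

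**6. With the change below.** If staff who know earlier allocations have no say in eligibility or timing, and the blind holds, the screener's chance is 33% for any block size.

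**The case against.** The strongest objection is that the mechanism is assumed. The documents describe a central list and never mention blocks. Stratification alone does not make a list predictable. Block rules or a separation of roles may stand in the SAP, the Blinding Plan or the missing end of Section 3.2, so their absence here is not a defect of the plan. This stands, and it makes the predictability part of the point conditional.

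The existing safeguards also count. Allocation is central, subjects complete VAS and ODI themselves, the opioid stratum comes from the e-diary, and SI-joint and facet exclusions rest on listed criteria or a diagnostic block. No text suggests that staff would coach subjects on baseline scores.

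A reader might be tempted by four stronger readings, none of which the documents support:

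- **That unblinded staff can foresee the next arm.** This needs small or fixed blocks whose size the site knows, and neither is shown.
- **That the guess rates are 61%, 56% and 53% for blocks of 3, 6 and 9.** Those are averages over completed blocks. Four subjects cannot complete a block of 6 or 9.
- **That small strata cause the problem.** For blocks of 6 or more, a stratum of 4 is less predictable than one of 12 (44% against 56% for blocks of 6). Predictability rises as strata fill blocks.
- **That every unblinded person knows every earlier allocation.** That fits the designee. An injector knows only the subjects he or she injected.

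What the objection does not remove is the permission itself. It is explicit, appears twice, and carries no limit in the available text.

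**Conclusion.** The point holds in conditional form. Established from the text: unblinded personnel may screen, the designee who keeps the assignment records is among them, and no available rule keeps that person away from later subjects' eligibility or timing. Not established: that the next arm is predictable, or that any selection would follow.

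Under fixed permuted blocks of known size, the gain over chance in an average stratum of 4 is about 21 points for blocks of 3 (54 − 33), 11 for blocks of 6 (44 − 33) and 6 for blocks of 9 (40 − 33, unrounded 6.3). It is larger where strata fill blocks. Varying block sizes hidden from sites would remove most of the argument. These figures measure how well an arm could be guessed, not the size of any bias in the treatment comparison. The change is still worth making, because it narrows a route to selection under any restricted scheme at little cost.

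**What to change.** Amend Section 5.5 and the matching synopsis text. Once a site has treated its first subject, unblinded personnel perform only technical screening procedures. Blinded staff administer baseline VAS and ODI, decide eligibility and request randomization. Section 6.6.3 and note f to Table 3, which only prefer a blinded evaluator for the neurological examination before the diagnostic injection, need a matching line.

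Separately, confirm in the SAP or Blinding Plan that block sizes vary and are concealed from sites, without disclosing them in a document that sites hold.

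The cost is protocol and blinding-plan wording. Blinded assessors are already required for follow-up at each site, so the practical downside is some scheduling burden at small sites.

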5.6 Treatment Compliance

All subjects in this study will undergo an injection into a single lumbar disc with either rexlemestrocel-L in freeze media ("rexlemestrocel-L alone"), rexlemestrocel-L cells in freeze media mixed with HA ("rexlemestrocel-L + HA"), or saline.

Each qualified subject will be randomized to one of 2 active treatment arms (rexlemestrocel-L alone or with HA) or to the saline control arm. All subjects will receive a single injection with the study product injected directly into the nucleus pulposus of the index level.

Any randomized subjects who, upon re-examination just prior to the injection procedure, do not meet the inclusion criteria or withdraw consent prior to treatment, will be considered randomized not-treated and will not receive treatment.

Throughout the study, the assigned unblinded CRA will monitor compliance with the treatment assignment, review and verify all investigational product accountability records and inventory at each participating investigational center.

6. STUDY PROCEDURE

6.1 Visit Schedule and Assessments

Table 3 shows all planned assessments, which are marked with an "X" for the visits at which they are performed. Subjects should be seen for all visits on the designated days or within the given windows for those visits. The study assessment schedule outlines all procedures to be performed on subjects at the scheduled visits.

In order to minimize variability in evaluations, ideally, the same personnel should perform the same tests and assessments on all the subjects at a given trial site, if possible.

Sites are required to access the interactive web response system (IWRS) at the beginning of the screening period to obtain a screening number. Sites are also required to access IWRS at the conclusion of the screening period to register the subject status. If the subject does not meet all inclusion and exclusion criteria, the subject will be considered a screen failure. If the subject meets all inclusion and exclusion criteria, the subject must be randomized a minimum of 7 days prior to treatment (Day 0) to allow time for shipment of investigational product to the site. In addition, treatment must be administered no later than 30 days following randomization.

Assessment	Screen/ Baseline ^b Visit 1 Days -105 to 0 ^a	Visit 2 Day 0 Treatment Injection ^w (7-30 days post- Randomiz ation)	Visit 3 1 Month (± 14 Days) ^a	Visit 4 3 Months (± 14 Days) ^a	Visit 5 6 Months (± 30 Days) ^a	Visit 6 12 Months (± 60 Days) ^a	Visit 7 18 Months (± 60 Days ^a	Visit 8 24 Months (± 60 Days ^a	Visit 9 36 Months (± 60 Days ^a	Unscheduled Visit ^c
Informed consent and privacy forms (e.g., HIPAA) ^d	Х	—	—	—	—					
Inclusion/exclusion criteria	Х	Х		_						
Demography and smoking history	X	_			_					
Medical & surgical histories	X				_					
Alcohol and Substance Abuse	X									
Questionnaire										
Mental Illness/Incompetence	Х									
Questionnaire										
Pain Catastrophizer Scale	Х									
SCORE or MORES assessment	X °									
Disease targeted, abbreviated PE e	Х	Х	Х	Х	X	X	Х	Х	Х	
Neurological Examination	Xf	X g	Х	Х	Х	Х	Х	Х	Х	Х
Targeted PE to rule out SI joint pain h	Х									
Vital signs, seated, if possible	Х	Xi	Х	Х	Х	Х	Х	Х	Х	Х
Height, weight, and BMI	Х	Х	Х	Х	Х	Х	Х	Х	Х	Х
Hematology	Х	—	Х	_	_	Х		Х	Х	
Chemistry Panel	Хj	—	Х	—	_	Х		Х	Х	
HIV	Х		_	_	_	_				
Pregnancy Test ^k	Х	X	_	_	_	_				
Flow Class I and II % PRA with specificity testing and DSA ¹	Х		—	—	—	Х		Х	Х	
MRI scan ^m	Х	_	_	_	_	Х	Х	Х	Х	
Flexion/extension x-ray m	X ⁿ		Х	Х	Х	Х	Х	Х	Х	
AP, lateral x-rays ^m	X ⁿ	_	Х	Х	Х	Х	Х	Х	Х	

Table 3: Schedule of Assessments and Procedures^a

CONFIDENTIAL

Clinical Study Protocol Study MSB-DR003

Assessment	Screen/ Baseline ^b Visit 1 Days -105 to 0 ^a	Visit 2 Day 0 Treatment Injection ^w (7-30 days post- Randomiz ation)	Visit 3 1 Month (± 14 Davs) ^a	Visit 4 3 Months (± 14 Davs) ^a	6 Months (± 30 Days) ^a	12 Months (± 60 Days) ^a	Visit 7 18 Months (± 60 Days ^a	Visit 8 24 Months (± 60 Days ^a	Visit 9 36 Months (± 60 Days ^a	Unscheduled Visit ^c
Lumbar spine DEXA ^o	Xp	ationy	Daysj	Daysj	Daysj	Daysj				
Leg pain assessments VAS	X q,r		Х	Х	Х	Х	Х	Х	Х	Х
Low back pain assessment VAS (average and worst pain over 24 hours)	X d'i	—	X	X	X	X	X	X	X	Х
Oswestry Disability Index (ODI) Questionnaire	X q	—	Х	Х	Х	Х	Х	Х	Х	Х
Self-Assessment of Treatment (SAT) Questionnaire		—	Х	Х	Х	Х	Х	Х	Х	
EQ5D	X q	_	X	Х	X	X	X	Х	X	
iMTA Productivity and Cost Questionnaire (iPCQ)	X q	—	Х	Х	Х	Х	Х	Х	Х	
Patient-reported Utilization Questionnaire	Х	—	—	—	—	Х	Х	Х	Х	
Diagnostic medial branch block ^s	Х			_	—	_				
Disc Injection to Confirm Intact Annulus	Xt	—	—	—	—	—				
Discography Procedure, if required	X bb									
Randomization	Xu		_	_	_					
Collection of Pharmacoeconomic Data ^v	Х	—	—	—	—	Х		Х	Х	
Treatment Injection		Xw								
Subject e-Diary Reminder	X ×	—	X ^y	X ^y	X ^y	X ^y	Х	Х	Х	
Subject e-Diary Completion ^z	X ×	_	Х	Х	Х	Х	Х	Х	Х	
Concomitant treatment aa	Х	Х	Х	Х	Х	Х	Х	Х	Х	Х
AE evaluation	X	Х	X	Х	X	Х	Х	Х	X	Х

a. All clinic visits are calculated from Visit 2/Day 0.

Version 6.0

Clinical Study Protocol Study MSB-DR003

- b. For subjects who are re-screened, all screening assessments should be repeated with the exception of the following:
 - **Diagnostic medial branch block**: if performed within 6 months prior to injection of study treatment (with documentation indicating no clinically significant facet pain in accordance with exclusion #42)
 - SI joint injection to determine SI joint pain (not required for all subjects): within 6 months prior to injection of study treatment (with documentation indicating no clinically significant SI joint pain in accordance with exclusion criteria #31)
 - Diagnostic injection to confirm intact annulus: if performed at least 2 weeks but no longer than 6 months prior to injection of study treatment
 - MRI: if performed within 6 months prior to injection of study treatment
 - **DEXA:** if performed within 6 months prior to injection of study treatment
 - AP, lateral and flexion-extension x-rays: if performed within 6 months prior to injection of study treatment and according to study-defined procedure
- c. Low back pain VAS (average and worst pain over 24 hours), ODI, vital signs, height, weight, concomitant treatment, neurological exam and AE evaluation are required at all unscheduled visits. All other assessments may be performed at the discretion of the investigator. For any subjects who are planning a post-treatment intervention during the course of the study, every effort should be made to schedule an unplanned study visit within a 30-day time window prior to the intervention. During this pre-intervention visit, all assessments and activities regularly performed at Visits 3-9 will be performed, with the exception of imaging assessments, hematology, chemistry panel, and Flow Class I and II % PRA with specificity testing and DSA. If the subject's originally planned assessment timepoint falls within 30 days prior to the post-treatment intervention, the unplanned study visit will not be necessary.
- d. Subjects will complete the informed consent process for Study MSB-DR003 at Screen/Baseline
- e. Disease targeted/abbreviated PE to include but not limited to examination of the musculoskeletal system.
- f. During screening, the neurological exam will be performed twice: one prior to the diagnostic injection to confirm an intact annulus and once after the diagnostic injection to assess if the injection procedure has resulted in any neurologic changes. The neurological exam prior to the diagnostic injection can be performed by the unblinded or blinded evaluator, but preferably the blinded evaluator. The post-diagnostic injection exam will be performed by the health care professional performing the injection procedure; this person may or may not be blinded.
- g. Neurological exam to be performed post treatment injection, prior to discharge to assess if the injection procedure has resulted in any neurologic changes. This will be performed by the unblinded health care professional performing the injection procedure, to avoid the potential unblinding of the blinded evaluator.
- h. If findings are inconclusive, the investigator may perform a diagnostic injection of anesthetic to the SI joint (Section 6.4.6).
- i. To be performed prior to the procedure and then following the procedure prior to discharge.
- j. Screening Chemistry Panel includes: albumin, alkaline phosphatase, ALT, AST, BUN, creatinine, hsCRP, chloride, direct bilirubin, GGT, glucose, lactic dehydrogenase, sodium, potassium, phosphorous, total bilirubin, total calcium, carbon dioxide, total cholesterol, total protein and uric acid
- k. For women of child bearing potential. A serum pregnancy test will be analyzed by the central laboratory at screening. An additional urine pregnancy test will be performed prior to administration of study treatment to confirm a negative result. If the urine pregnancy test is positive, study treatment will not be administered that day, and the result will be confirmed by a serum pregnancy test.
- 1. Specificity testing and DSA only for those Class I or II PRA results \geq 5%. Specificity testing and DSA results will be blinded until the end of the study.
- m. MRIs and radiographs should be taken on the same machine using the same settings, and in accordance with the radiographic guidelines provided, from baseline to completion of the study to minimize potential differences in results caused by use of different machines. Radiographic evaluations may vary for a given subject depending on the time of day the assessments are made. Therefore, for each subject, all radiographic evaluations of a specific type (e.g., X-ray) should be taken at the same time of day at each assessment if possible, preferably in the morning. MRIs and radiographs will be evaluated by a core imaging provider for the criteria noted in the inclusion & exclusion criteria. All other radiographic evaluations at screening will be assessed by the investigator. Evaluation of the change in macromolecular content and hydration of the treated disc will be performed on a subset of subjects where T1 rho and T2 mapping capability is available.
- n. Screening DEXA scans and AP, lateral and flexion-extension x-rays performed according to study-defined procedure may be performed up to 6 months prior to procedure.
- o. Any female subject with a SCORE of ≥6 or male subjects with a MORES of ≥6 will require a lumbar spine DEXA scan to be performed. Similarly, subjects who are considered at risk, as defined in exclusion criterion #4 (Section 6.4.5), will be required to have a DEXA scan at screening, regardless of SCORE value.

Clinical Study Protocol Study MSB-DR003

- p. The DEXA scan will measure bone mineral density and determine whether or not the subject is considered to have severe osteoporosis. A T-score that is within \leq -2.5 standard deviations from the standard will exclude a potential subject from participating in this study.
- q. For subjects who are re-screened, this patient-reported outcome must be performed at least 2 weeks after the most recent diagnostic injection procedure (i.e., diagnostic disc injection to confirm intact annulus, medial branch block and SI joint injection, if deemed necessary).
- r. At screening, the VAS evaluation must be administered before any diagnostic injections or at least 2 weeks following any injections to relieve pain.
- s. If a previously performed medial branch block on and/or SI joint injection was performed up to 6 months prior to injection (with documentation indicating no facet pain and/or SI joint pain), this does not need to be repeated at screening
- t. There must be at least a 2-week "washout" period following the diagnostic disc injection and prior to the injection of study treatment (i.e., any injection of contrast media into the disc must be performed at least 2 weeks prior to the rexlemestrocel-L injection procedure). If an injection of contrast media was performed within 6 months prior to the rexlemestrocel-L injection procedure and presence/absence of full thickness annular tears is documented, it will not have to be repeated.
- u. Must occur at least 7 days prior to treatment injection to allow for investigational product to be shipped to the site, but not more than 30 days prior to treatment injection.
- v. A subject's informed consent in this study will include permission for the release of any non-study-related medical records that will provide data for pharmacoeconomic analyses. However, this is optional and will not impact a subject's participation in the study.
- w. Includes recording procedural information. Treatment injection must occur no later than 30 days after randomization.
- x. At a timepoint after informed consent, subjects should be instructed to complete the e-diary for 2 weeks. Subject e-diary should be completed each day for 2 weeks after signing informed consent but prior to diagnostic injection to confirm intact annulus unless a historical diagnostic injection or e-diary is used.
- y. Subjects should be contacted, either automatically by IWRS or by the site, approximately 2 weeks prior to each post-treatment visit as a reminder to complete daily pain medication patient e-diaries.
- z. Please see sections 6.7.2, 6.7.3, and 6.7.6 for collection details on VAS, ODI and pain medication. .
- aa. Subject will be asked about all medications being taken, including pain medications (e.g., NSAIDs, opioids), tricyclic anti-depressants, membrane stabilizers/anticonvulsants, sleeping pills, muscle relaxants, etc. and other treatments (chiropractic, acupuncture, physical therapy, spinal injections, etc.) used to treat their back pain.
- bb. A discography procedure may be performed to determine the index level. procedure may be required.

a discography

